### **10.3. Statistical analysis**

Collected data will be analyzed with SPSS (PASW statistics). Descriptive statistics is used for testing potential differences between the groups at baseline (chi-square tests for categorical variables, independent samples t-tests for continuous variables). We use independent samples t- tests to compare the mean difference of change from pre- to post-treatment between the two treatment groups, and analyses of covariance (ANCOVA) to compare these differences while adjusting for variables that differed between the groups at baseline as covariates. For the non-controlled extension part of the study, we use paired sample t-tests to assess change from baseline to 6-months follow-up, and analyses of variance (ANOVA) for repeated measures to assess change in symptom scores from baseline to post-treatment from the RCT and at 6 months follow-up after group treatment for all participants. We will estimate standardized effect sizes (ES) of the treatment by dividing the mean difference in symptom scores from pre-to post treatment with the pooled standard deviation (SD) of the respective measure, reporting as Cohen's d. The significance threshold is set at 5% (two-tailed) and we use two-sided 95% confidence intervals (CI). Analyses are restricted to participants with actual responses on each of the respective questionnaires, i.e., will exclude participants with missing values analysis-by-analysis.

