## 5. INVESTIGATIONAL INTERVENTION

### 5.1. Elements of the DBT-based group therapy

The structured skills group treatment uses elements from DBT such as psychoeducation, acceptance, mindfulness, and functional behavioral analysis, such targeting symptoms and functional problems common in ADHD. It consists of 14 weekly group sessions, each lasting two hours separated by a 15-minute break. Each group includes 7-9 patients with ADHD and two therapists. Group sessions follow a structure with manualized instruction for the therapists and workbook for the patients.

A typical session begins with introducing a new mindfulness exercise performed together in the group. The first part of the session then focuses on feedback on last week's homework of skill training, while the second part introduces a new topic and related homework for the next week. The topics for the different sessions include psychoeducation, mindfulness, functional behavioral analyses, and how to understand and manage different symptoms and aspects of ADHD, e.g. impulsivity, addiction, emotional

regulation, self-esteem, and relation to others. Interaction between the participants is important, and the therapists should encourage and balance their feedback and discussion during the session. After each group session, patients will receive 15-20 minutes of individual coaching with one of the therapists. This is an add-on element according to a Swedish adaptation of the program. The coaching focuses on adherence to homework related to each participant's situation and pre-defined goals.

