# **10. STATISTICAL CONSIDERATIONS**

## **10.1. Determination of sample size**

To assess the required number of participants, a power analysis was calculated on the basis of literature indicating the similar DBT-group intervention in a smaller study showed a significant reduction in ADHD measures in the skills training group (n=19) compared to the control group (n=18) (Hirvikoski et al 2011). To address the hypothesis of superiority of the DBT-based group treatment on different outcome measures and an assumed difference in at least 10% between means (and SD 15%) of the two independent groups, we estimated a need of sample size of about 50 participants in each group (alpha = .05, power = .9) (<https://clincalc.com/stats/samplesize.aspx>). To account for dropouts up to 20%, more patients are needed, resulting in a total of 120 participants.

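### DBT-bGT is delivered in about 6 to 8 interacting therapy groups, but the sample size and the planned t-test and ANCOVA treat participants as independent; with a positive therapy-group correlation, size and power can differ from those stated

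*Protocol*

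**What the plan says.** - **Delivery (Section 5.1).** "Each group includes 7-9 patients with ADHD and two therapists". Peer influence is part of the treatment: "Interaction between the participants is important, and the therapists should encourage and balance their feedback and discussion during the session". Section 3.2 gives a slightly different size, 7 to 10 participants with two leaders.
- **Control (Section 5.2).** Treatment as usual is not standardised, may differ between patients and between clinics, and is not described as group-delivered.
- **Randomisation (Section 10.2).** Allocation is individual, 1:1, by lottery at each site. A draw is held once a site has enough participants to form two groups, so each draw is a batch that yields one DBT-bGT group and one TAU group.
- **Sample size (Section 10.1).** It rests on "an assumed difference in at least 10% between means (and SD 15%) of the two independent groups", which gives "about 50 participants in each group" with "alpha = .05, power = .9". Dropout of up to 20% brings the total to 120. No ICC, design effect or number of therapy groups is stated.
- **Analysis (Section 10.3).** "We use independent samples t- tests to compare the mean difference of change from pre- to post-treatment between the two treatment groups". ANCOVA then adjusts for variables that differed at baseline. "The significance threshold is set at 5% (two-tailed"). No therapy-group, therapist, site or batch term appears.

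**The concern.** Participants in one therapy group share two therapists and are encouraged to affect one another over 14 weeks. Their change scores may therefore be correlated, which individual randomisation does not prevent, because the correlation arises after allocation. TAU participants have no such grouping, so the design is partially nested.

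An independent-samples t-test sets this correlation to zero. If it is positive, the variance of the DBT-bGT mean is understated, confidence intervals are too narrow, and the two-sided 5% test can reject too often. Adjusting for baseline variables does not restore the missing variance component. The 90% power also belongs to a design with no clustering. Both primary outcomes, BRIEF-A and DERS, are affected.

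This is not a detail left open for a statistical analysis plan. The protocol names the test and sizes the trial for independent observations, so a plan that added a group term would be changing the stated analysis.

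**Working it through.** **1. The plan's own figure.** Difference 10, SD 15, two-sided 5%, power 0.90 (Sections 10.1 and 10.3).

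n per arm = 2 × (1.960 + 1.282)² × (15/10)² = 47.3, so 48. Then 48 / 0.80 = 60 per arm, 120 in total. The stated figure reproduces under independence. With 48 analysed per arm the ordinary t-test has power 0.898; with 50 it has 0.910.

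**2. Number of therapy groups.** 60 in the active arm at 7 to 10 per group gives 60/10 = 6 to 60/7 = 8.6, so about 6 to 8 groups. After 20% loss, 48 analysed is 8 groups of 6 or 6 groups of 8.

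**3. Assumptions not in the documents.** Therapy-group ICC of 0.02, 0.05 or 0.10, in the DBT-bGT arm only; TAU unclustered.

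**4. Size of the planned test, no shared batch variance.** With m analysed per group:

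- design effect in the DBT-bGT arm, DE = 1 + (m − 1) × ICC
- variance ratio for the difference, R = (DE + 1)/2
- true size = 2 × [1 − Φ(1.96/√R)]

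| ICC | m = 6: DE, R, size | m = 8: DE, R, size |
|---|---|---|
| 0.02 | 1.10, 1.050, 5.6% | 1.14, 1.070, 5.8% |
| 0.05 | 1.25, 1.125, 6.5% | 1.35, 1.175, 7.1% |
| 0.10 | 1.50, 1.250, 8.0% | 1.70, 1.350, 9.2% |

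Allowing for simulation results a little below the formula, the ranges are about 5.6-5.8% / 6.2-7.1% / 8.0-9.2%.

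**5. Size when batches also share variance.** Each draw feeds both arms, so variance common to a batch (assumed share b of the total) cancels from the difference, but the unadjusted t-test still counts it as error. Approximately, R = 1 + (m − 1) × ICC/2 − b. For b of 0.05 to 0.10 and m of 6 or 8:

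- ICC 0.02: R = 0.95 to 1.02, size 4.4-5.2%
- ICC 0.05: R = 1.025 to 1.125, size 5.3-6.5%
- ICC 0.10: R = 1.15 to 1.30, size 6.8-8.6%

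Simulation gives about 4.5-5.3% / 5.5-6.6% / 6.9-8.6%.

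**6. Power of a valid test.** With k groups, v₁ = DE/48 for the DBT-bGT mean and v₂ = 1/48 for TAU (SD units). Satterthwaite df = (v₁ + v₂)² / [v₁²/(k − 1) + v₂²/47]. Noncentrality = (10/15)/√(v₁ + v₂). No batch variance is assumed.

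| ICC | 8 groups of 6: df, power | 6 groups of 8: df, power |
|---|---|---|
| 0 | 24.4, 0.880 | 18.1, 0.870 |
| 0.02 | 22.7, 0.862 | 16.3, 0.843 |
| 0.05 | 20.7, 0.835 | 14.3, 0.801 |
| 0.10 | 18.2, 0.789 | 12.2, 0.734 |

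The first row isolates the df cost: 0.898 falls to 0.87-0.88 with no correlation at all. The rest of each drop is due to the ICC.

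**7. No dropout.** With 60 analysed per arm and ICC 0.05, the same formula gives 0.896 (8 groups) and 0.865 (6 groups).

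**The case against.** **The ICC is assumed.** This stands. A reader might infer that the 90% power is simply not delivered and that the p-values are too small. The documents do not support that as fact. At ICC 0.01 with 50 analysed per arm and 7 to 10 per group, normal-approximation power is still 0.903-0.907 and size about 5.4-5.5%. On that basis power falls below 0.90 only once the ICC exceeds about 0.013 (groups of 10) to 0.019 (groups of 7).

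**Batch randomisation offsets the inflation.** This stands in part. At ICC 0.02 the offset can bring size back to 5% or below. At ICC 0.10 an excess remains.

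**Some of the power loss belongs to the cluster-aware test.** True: two to three points are df cost. That cost comes from having only 6 to 8 groups, and a valid analysis has to bear it.

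**Dropout may be below 20%.** True, and power is then higher. Lower dropout does not remove the size problem.

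**Two further inferences go beyond the text.** One is that every group has its own distinct pair of therapists. The protocol says two per group, and therapists could lead several. The other is that the paired and repeated-measures tests in the extension are similarly affected. No size has been established for that uncontrolled phase, and the point does not rest on it.

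**Conclusion.** The point holds in conditional form. The protocol specifies group delivery with intended interaction, then fixes a sample size and tests that assume independence, with no therapy-group or site/batch term.

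At 48 analysed per arm and assumed ICCs of 0.02 / 0.05 / 0.10, the size departure ranges from negligible (once batch variance is allowed for) to about 9% against a nominal 5%. Power of a valid test ranges from about 86% down to 73%, against the stated 90%. These figures rest on the assumed ICCs, 6 to 8 groups of equal size, and TAU outcomes that are not clustered apart from any shared batch effect. The direction of the therapy-group effect follows from any positive ICC; the net error of the unadjusted test also depends on the batch variance.

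**What to change.** - **Section 10.3.** For both primary outcomes, replace the t-test and ANCOVA with a partially nested mixed model (SPSS MIXED, within the software already named). Include a random therapy-group effect in the DBT-bGT arm only, adjustment for site or randomisation batch in both arms, residual variance allowed to differ by arm, and Satterthwaite or Kenward-Roger df. The batch term matters: without it, batch variance is charged to the therapy-group effect and the test becomes conservative.
- **CRF.** Record therapy-group and batch identifiers. Both are known from the site draw.
- **Section 10.1.** Replace the single 90% with a sensitivity range over assumed ICC 0.02-0.10 and 6 to 8 groups: about 73-86% at 48 analysed per arm. Label the ICC as an assumption, and use one therapy-group size in Sections 3.2 and 5.1.

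The cost is protocol wording and two identifier variables, with no extra enrolment. The downside is slightly wider confidence intervals and a less favourable stated power.

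### Section 10.3 gives two unranked analyses of change and lets chance baseline differences choose the ANCOVA covariates, so the outcome's own baseline score is usually left out and precision is lost

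*Protocol*

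**What the plan says.** Protocol Section 10.3 sets out three steps.

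- Baseline comparison: "Descriptive statistics is used for testing potential differences between the groups at baseline", by chi-square tests for categorical variables and t-tests for continuous ones.
- Unadjusted comparison: "We use independent samples t- tests to compare the mean difference of change from pre- to post-treatment between the two treatment groups".
- Adjusted comparison: an ANCOVA of the same differences, "adjusting for variables that differed between the groups at baseline as covariates".

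The two comparisons are joined by "and". Neither is called primary or deciding, and no covariate is fixed in advance. The significance level is 5%, two-sided.

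Three other parts bear on this. Section 7.1 defines both primary outcomes (BRIEF-A and DERS) as changes from baseline, so a baseline score is planned for every participant. Section 10.2 has the lots drawn separately at each site. Section 10.1 sizes the trial on "an assumed difference in at least 10% between means (and SD 15%) of the two independent groups" with "alpha = .05, power = .9", and concludes: "we estimated a need of sample size of about 50 participants in each group".

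**The concern.** A baseline test in a randomised trial asks whether a difference is due to chance, when the allocation already guarantees that it is. The result says nothing about whether a variable predicts outcome, which is what makes a covariate worth having. The rule can therefore admit an irrelevant variable that differs by luck and shut out the outcome's own baseline score, likely a strong predictor, because it is balanced.

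Two things are at stake. One is precision: an unadjusted change score carries avoidable noise unless the correlation between baseline and 14 weeks is close to 1. The other is clarity: the report will hold two results for each primary outcome, with the second model shaped by the trial's own data. When the baseline score does differ, the two can disagree, and nothing in the protocol says which one counts.

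**Working it through.** **Inputs.** Difference 10, SD 15, alpha 0.05 two-sided, power 0.90 and 20% dropout come from Section 10.1. The correlation rho between baseline and 14-week scores is not in the protocol, so a range is assumed. Section 10.1 does not say whether SD 15 belongs to the raw score or to the change, so both readings are worked. Equal SDs before and after treatment and independent participants are assumed.

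**1. The protocol's own figure.** n per arm = 2 × (1.960 + 1.282)² × 15² / 10² = 47.3, rounded up to 48, against a stated figure of about 50. With dropout, 48 / 0.8 = 60 per arm, or 120 in total. The figure reproduces as a simple unadjusted two-sample calculation.

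**2. Variance.** With common SD s:

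- change score: 2(1 − rho)s²
- ANCOVA with baseline: (1 − rho²)s²
- ratio: (1 − rho²) / [2(1 − rho)] = (1 + rho)/2

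This is 0.70, 0.75, 0.80 and 0.85 for rho 0.4, 0.5, 0.6 and 0.7: 30%, 25%, 20% and 15% less variance. At rho 0.8 the saving falls to 10%.

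**3. Power at 48 per arm** (non-central t, difference 10).

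| rho | SD 15 = raw score: t-test | SD 15 = raw score: ANCOVA | SD 15 = change: t-test | SD 15 = change: ANCOVA |
|---|---|---|---|---|
| 0.4 | 84% | 94% | 90% | 97% |
| 0.5 | 90% | 96% | 90% | 96% |
| 0.6 | 95% | 98% | 90% | 95% |
| 0.7 | 99% | 99.5% | 90% | 94% |

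For example, on the raw-score reading at rho 0.4 the SD of change is 15 × √(2 × 0.6) = 16.4 and the ANCOVA residual SD is 15 × √(1 − 0.16) = 13.7.

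**4. Does the covariate rule recover the loss?** If "differed" means p < 0.05, a balanced lottery flags the baseline score in about 5% of trials, so it is left out in about 95%. Simulation (40,000 trials per setting, 50 per arm, raw-score reading, baseline score the only candidate) gave this power:

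| rho | t-test | adjust only if baseline differs | always adjust |
|---|---|---|---|
| 0.3 | 80.0% | 81.4% | 93.5% |
| 0.5 | 90.7% | 91.6% | 96.5% |

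The rule recovers almost nothing.

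**5. Type I error.** Over all simulated trials the adjust-if-different rule rejects in about 4–5%, and counting a rejection by either the t-test or the selected ANCOVA gives about 5%. Within trials where the baseline score is flagged, the t-test rejects in about 24%, 18% and 13% at rho 0.3, 0.5 and 0.7 (separate simulations ranged over 23–24%, 18% and 12–14%). The ANCOVA in those same trials stays at about 5%.

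**6. How often chance sets the model.** For k independent baseline variables tested at 5%, the chance that at least one differs is 1 − 0.95^k: 34% for 8, 40% for 10, 64% for 20. This is illustrative: the protocol does not give the number of tests, and its rating scales are unlikely to be independent.

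**The case against.** The strongest defence is that neither listed analysis is invalid. A change-score t-test is unbiased over the randomisation, and on the raw-score reading it meets the 90% target, to rounding, once rho reaches 0.5. On the SD-of-change reading it has about 90% at every rho. When the baseline score is visibly imbalanced, the covariate rule does bring it into the ANCOVA, which then holds its error rate. An extra covariate picked up by luck does not by itself bias the treatment estimate. Finally, naming the deciding analysis is often left to a statistical analysis plan, which may exist.

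Much of this stands, and it rules out three stronger readings that a reader might infer.

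- *That the t-test is the primary analysis.* It is listed first, but Section 10.3 ranks neither.
- *That the rule inflates the trial's overall type I error.* With the baseline score as the only candidate, it does not. A search over many candidate covariates was not simulated, so no claim is made about that.
- *That the trial is underpowered.* That follows only on the raw-score reading with rho below 0.5, and the protocol settles neither.

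What does not stand is the appeal to an unseen analysis plan. The protocol states a rule for choosing covariates, and a later plan would have to contradict it to repair it. Nor does the ANCOVA in flagged trials fully answer the point: the t-test, with its distorted conditional error, is still reported beside it with no ranking.

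**Conclusion.** The concern holds as a stated, inferior analysis rule. Section 10.3 leaves two results unranked and lets chance differences choose the covariates, so the outcome's baseline score is usually omitted. The cost is 15–30% of the variance for rho between 0.7 and 0.4, less if rho is higher. On the raw-score reading of SD 15 that is worth 10 percentage points of power at rho 0.4 and under 1 point at rho 0.7. On the SD-of-change reading the target is already met and the gain is narrower intervals. The conditional error of the t-test matters only in the roughly one trial in twenty where the baseline score differs significantly; overall error stays near 5%. These sizes rest on an assumed rho, equal SDs and independent participants. The defect in the rule itself rests on none of them.

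**What to change.** In Section 10.3, name one primary analysis for each primary outcome: an ANCOVA of the 14-week score on arm, with that outcome's baseline score always included and site as a fixed covariate, because the lots are drawn within site. With baseline in the model, analysing the 14-week score or the change gives the same treatment estimate, so the outcome definition in Section 7.1 need not change. Describe baseline characteristics by arm without using significance tests to select covariates. Keep the change-score t-test as a sensitivity analysis at most. In Section 10.1, say whether SD 15% refers to the raw score or to the change.

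This takes a sentence or two, with no new data and no more patients, and should be settled before outcome data are analysed. It does not settle which BRIEF-A or DERS score (total or dimensional, self or informant) is decisive; that is a separate choice.

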**Main Inclusion and Exclusion Criteria:**

- Diagnosis of ADHD assessed by a trained specialist clinician according to the Diagnostic and Statistical Manual of Mental Disorders, 4th. Edition (DSM-IV) persisting in adulthood
- Unmedicated or stably medicated with any ADHD-medication.
- Between 18 and 60 years of age (all groups).
- Exclusion criteria are any ongoing psychiatric disorders and/or

psychosocial factors considered to clearly interfere with the patients' ability to participate in the group, i.e., ongoing substance or alcohol abuse, psychotic disorder, major depressive or manic episode, and suicidal behavior; organic brain damage, neurological diseases causing mental handicap, intellectual disability ( $IQ \leq 70$ ), and pervasive developmental disorder.

- Sample Size:** Estimated 120 patients
- Efficacy Criteria:** Measures of changes in the defined outcome measures between groups and pre-post individually at follow-up.
- Safety Criteria:** In case of SAE (severe adverse events), patient will be considered for exclusion and indicated treatment will be administered immediately.

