### **6.4. Criteria for patient discontinuation**

Patients may be discontinued from study treatment and assessments at any time. Specific reasons for discontinuing a patient for this study are:

- Voluntary discontinuation by the patient who is at any time free to discontinue his/her participation in the study, without prejudice to further treatment.
- Safety reason as judged by the Principal Investigator.
- Incorrect enrollment (i.e. the patient does not meet the required inclusion/exclusion criteria for the study)
- Related Serious Adverse Event

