#### **6.4.1 Procedures for discontinuation**

Patients who withdraw or are withdrawn from the study will continue clinical treatment as determined by their physician. Any reasons for withdrawing from the study will not impact the patient's clinical treatment.

Reason for discontinuation shall be recorded if reason is disclosed. The investigator is obliged to follow up any significant adverse events until the outcome is resolved.

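### Section 10.3 makes available cases the only analysis while up to 20% dropout is expected, and no section asks for outcome questionnaires once therapy has stopped

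*Protocol*

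**What the plan says.** **Analysis rule (Section 10.3).** "Analyses are restricted to participants with actual responses on each of the respective questionnaires", which the same sentence explains as a plan that "will exclude participants with missing values analysis-by-analysis". The main test is an independent-samples t-test "to compare the mean difference of change from pre- to post-treatment between the two treatment groups", so both a baseline and a week-14 score are needed. An ANCOVA adjusts for variables that differ at baseline. The section names no analysis set of all randomised participants and no other way of handling missing scores.

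**Expected loss (Section 10.1).** "To account for dropouts up to 20%, more patients are needed", giving 120 in total. Dropout is treated only as a loss of numbers.

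**How scores come to be missing (Sections 6.4 and 6.4.1).** "Patients may be discontinued from study treatment and assessments at any time". One listed reason is "Incorrect enrollment (i.e. the patient does not meet the required inclusion/exclusion criteria for the study)". After that, "Patients who withdraw or are withdrawn from the study will continue clinical treatment as determined by their physician". Section 6.4.1 also asks for the reason to be recorded and for significant adverse events to be followed up. It does not mention the week-14 or 6-month questionnaires. The synopsis adds: "In case of SAE (severe adverse events), patient will be considered for exclusion".

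**The concern.** Randomisation makes the two full arms comparable. It does not make the subsets that return a week-14 form comparable. The protocol itself gives reasons why loss could differ between arms:

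- Section 5.1 describes 14 weekly two-hour sessions with homework and individual coaching after each one.
- Section 5.2 describes TAU as the care the patient would have had outside the project, so there is little to drop out of.
- Section 3.2 gives the TAU arm delayed access to the group, which is a reason to stay.

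If leaving is related to how a person is doing, and more so in one arm, the estimated differences on BRIEF-A and DERS are shifted and recruiting more people does not correct it. The two primary outcomes may also rest on different subsets. The missing-data rule is written into the protocol, so this is not a detail left to a separate analysis plan. Week-14 scores that were never requested cannot be recovered at the analysis stage.

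**Working it through.** **1. The protocol's own sample size.** Inputs from Sections 10.1 and 10.3: difference 10, SD 15, two-sided alpha 0.05, power 0.90.

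n per arm = 2 × (1.960 + 1.282)² × 15² / 10² = 47.3, so 48. The protocol says about 50.

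48 / (1 − 0.20) = 60 per arm, or 120 in total, as stated. The sample size is not in error.

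**2. What the inflation does.** At the 20% ceiling, 0.20 × 120 = 24 people are left out and 96 are analysed (48 per arm). Power is 0.904 with 48 per arm and would be 0.955 with all 60 per arm assessed. The inflation protects power. It has no effect on bias.

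**3. Bias of the available-case difference.** In each arm let p be the share missing and g the mean change of completers minus that of dropouts (completers of the questionnaire). The full-arm mean is the completer mean minus p × g, so

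bias = p_DBT × g_DBT − p_TAU × g_TAU.

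The protocol gives only an overall ceiling for p and nothing on g. Everything below is assumption, shown as a range.

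**4. TAU losses at random (g_TAU = 0), no true effect, SD 15.** The SE is 15 × √(1/n₁ + 1/n₂): 3.06 for 48 v 48 and 3.09 for 42 v 54.

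| Missing, DBT v TAU | Analysed | g_DBT | Spurious difference | Two-sided error rate (nominal 5%) |
|---|---|---|---|---|
| 20% v 20% | 48 v 48 | 5 | 1.0 | 6.2% |
| 20% v 20% | 48 v 48 | 10 | 2.0 | 10.0% |
| 20% v 20% | 48 v 48 | 15 | 3.0 | 16.5% |
| 30% v 10% | 42 v 54 | 5 | 1.5 | 7.8% |
| 30% v 10% | 42 v 54 | 10 | 3.0 | 16.3% |
| 30% v 10% | 42 v 54 | 15 | 4.5 | 30.8% |

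The 30% v 10% rows still average 20% overall.

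**5. Selective loss in both arms, 20% missing in each.**

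- Equal gaps of 10: 0.2 × 10 − 0.2 × 10 = 0.
- Gaps of 10 (DBT) and 5 (TAU): 2 − 1 = 1 point in favour of DBT-bGT.
- Gaps of 5 (DBT) and 10 (TAU): 1 − 2 = −1 point, against DBT-bGT.

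**6. Would a model of baseline and week 14 alone repair this?** Suppose dropouts have the same baseline scores as completers but improve less. Baseline then carries no information about the missing change, and the model returns the available-case answer. Only collecting the scores, using informative auxiliary measures, or analysing under a departure from missing at random changes the estimate.

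**The case against.** The other side has a good case on several points, and most of it stands.

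- A reader might infer that this is a comparison of people who completed therapy. The text does not say so. Section 10.3 excludes on missing responses, with no attendance threshold, and a participant who leaves the group but returns the week-14 form is analysed. Section 6.4 permits treatment and assessments to end together but does not require it. Section 7.1 schedules assessments without an adherence condition, Section 4 has all participants reassessed at follow-up, and Section 9.1 wants reasons for omitted assessments noted.
- A reader might infer that wrongly enrolled participants, or those with a serious adverse event, are removed from the analysis. They may be discontinued or considered for exclusion, but no section says that scores already collected are dropped.
- A reader might infer that the bias favours DBT-bGT. Step 5 shows it can be zero or run the other way, and the documents do not settle it.
- Exclusion analysis by analysis keeps a person in every questionnaire they did answer. Scores are lost only to the analysis whose outcome is missing.
- A sensitivity analysis under other missing-data assumptions is ordinary content for an analysis plan, and its absence here is not itself a fault.

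What does not fall is the stated rule: available cases are the only analysis, dropout of up to 20% is expected, and nothing provides for outcome collection after therapy stops.

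**Conclusion.** The point holds in this limited form. The primary comparison is an available-case comparison, meaning completers of the questionnaire and not necessarily of therapy. It is unbiased only if missingness is unrelated to outcome given arm and any covariates, or if selective losses happen to cancel between arms. The protocol argues neither, and the burden differs between a 14-week group programme and TAU.

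The existence of the rule is certain. The bias is a risk whose size and sign cannot be derived from the documents. With 20% missing per arm, TAU losses at random and gaps of 5 to 15 points, it is 1 to 3 points, or 10% to 30% of the planned difference of 10. The larger figures need unequal dropout as well. This should be fixed, because it touches both primary outcomes and the repair is cheap. The documents do not support saying that the result will be wrong, or in which direction.

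**What to change.** 1. **Sections 6.4 and 6.4.1.** State that stopping group therapy, or being found wrongly enrolled, does not end outcome collection. The week-14 and 6-month questionnaires are still requested unless the participant withdraws from assessments. This concerns data collection only and leaves the clinical criteria as they are.
2. **Section 10.3, primary analysis.** Analyse week-14 BRIEF-A and DERS in all randomised participants as allocated. Use multiple imputation done separately by arm, with baseline scores and the other questionnaires as predictors, or a likelihood-based model. Leave the 6-month scores out or use them only within arm, because TAU participants have by then been offered DBT-bGT. With about 60 per arm, keep the imputation model small.
3. **Section 10.3, sensitivity.** Keep the available-case analysis as a sensitivity analysis. Add one that departs from missing at random, for the reason in step 6 of the working.

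Cost: some extra effort to send existing questionnaires to people who have stopped, some analysis work, and possibly a slightly smaller estimated effect. The sample size does not change, and each extra week-14 score obtained adds power, up to 0.955 if all are assessed.
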